## 9. STATISTICAL CONSIDERATIONS AND DATA ANALYSES

A statistical analysis plan (SAP) will describe the detailed statistical methods and analyses for this study.

All efficacy and safety measures over the course of both the parent and extension studies will be presented by the parent study treatment group using descriptive statistics. No formal treatment comparisons will be performed for this extension study. Continuous data will be summarized by means, standard deviations, medians, maximum, minimum, and number of patients. Categorical data will be summarized by counts and percentages.

### **9.1. Randomization Methods**

This is a single-arm, open-label extension study; patients are not randomized. All patients who have entered the extension study will be treated with open-label relugolix and low-dose hormonal add-back therapy for 28 weeks.

### **9.2. Analysis Populations**

Efficacy data analyses will be performed on the modified Intent-to-Treat (mITT) Population, defined as all patients who were randomized in a parent study (MVT-601-3101 or MVT-601-3102) and who have received any amount of randomized study drug.

Safety data analyses will be performed on the Safety Population, defined as all patients who were randomized in a parent study and who have received any amount of randomized study drug.

The analysis methods for safety and efficacy endpoints are the same as those used for the parent studies, unless otherwise specified in the SAP.

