## 1. PROTOCOL SYNOPSIS

Study Title	SPIRIT EXTENSION: An International Phase 3 Open-Label, Single-Arm, Safety and Efficacy Extension Study to Evaluate Relugolix Co-Administered with Low-Dose Estradiol and Norethindrone Acetate in Women with Endometriosis-Associated Pain
Protocol Number	MVT-601-3103
Location	Multinational, including North and South America, Europe, Africa, New Zealand, and Australia
Study Centers	Approximately 320 sites
Study Phase	Phase 3
Target Population	Women aged 18 to 51 years diagnosed with endometriosis-associated pain
Number of Patients Planned	Approximately 800
Study Objectives	
In women with endometriosis-associated pain, the study objectives are as follows:
 
Primary Efficacy Objective
 
 
To evaluate long-term efficacy of relugolix 40 mg once daily co-administered with low-dose estradiol and norethindrone acetate for up to 52 weeks, among patients who previously completed a 24-week treatment period in one of the parent studies (MVT-601-3101 or MVT-601-3102), on endometriosis-associated pain.
 

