
Study Design
 
The SPIRIT EXTENSION study is an international phase 3 open-label, single-arm, long-term efficacy and safety study that will enroll eligible patients who have completed their participation in one of the phase 3 randomized, double-blind, placebo-controlled parent studies (MVT-601-3101 or MVT-601-3102). All patients will receive oral relugolix 40 mg once daily co-administered with low-dose estradiol 1.0 mg and norethindrone acetate 0.5 mg for up to 28 weeks. Approximately 800 women with endometriosis-associated pain will be enrolled. The objectives of the study are to evaluate long-term efficacy and safety through up to 52 weeks of treatment (including treatment during the parent study) of relugolix co-administered with low-dose estradiol/norethindrone acetate. Eligible patients will have completed participation in one of the parent studies and consented to participate in this extension study. Baseline procedures will be done at the same visit for this extension study (referred to as the “Week 24/Baseline visit” in this study) that coincides with the Week 24 visit from the parent study, and will be defined as the date of completion of the last Week 24 procedure in the parent study. The Week 24/Baseline visit will include vital signs, physical examination, laboratory assessments, a 12-lead electrocardiogram (ECG), bone densitometry, patient-reported outcome assessments, and endometrial biopsy (if required). When Week 24 procedures in the parent study have been completed, the investigator will assess patient eligibility for participation in the open-label extension study. The eligibility assessment will be based on data available at the Week 24/Baseline visit. No MVT-601-3103 study procedures will be performed until the consent form for this extension study is signed.
 
Patients will have received their last dose of study drug in the parent study on the day prior to the Week 24/Baseline visit, and will receive their first dose of study drug for this extension study in the clinic after the patient is determined to be eligible for this extension study and has provided informed consent to participate. Therefore, results of testing required for eligibility must be available on or prior to the Week 24/Baseline visit. The administration of the first dose of study drug for MVT-601-3103 will define enrollment into this study. Study participants will then take the open-label study treatment (relugolix 40 mg co-administered with estradiol 1.0 mg and norethindrone acetate 0.5 mg) orally once daily for 28 weeks.
 
During the 28-week Open-Label Treatment Period and the ~30-day Follow-Up Period, patients will continue to record study treatment, assessment of pain using the NRS, menstrual bleeding, analgesic use, and the functional effects of endometriosis-associated pain (sB&B) in the electronic diary (eDiary). Only study-specific rescue analgesic medications should be used starting with the Week 24/Baseline visit and through the Follow-Up visit and these medications will be taken for control of pain and not prophylactically. Health-related quality of life questionnaires; PGIC for dysmenorrhea, NMPP, and dyspareunia; and PGA for pain and function will be completed during the visits on an electronic tablet or on paper, according to the Schedule of Activities (Section 1.1).
 
At the Week 36 visit and Week 52/Early Termination visit, each patient will have an assessment of bone mineral density via dual-energy x-ray absorptiometry (DXA).
	

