Criteria for Evaluation	
Descriptive assessments of long-term efficacy and safety will be made between the parent study Baseline and the end of the extension study (Week 52) for the following parent study treatment groups:
 
 
Parent Study Group A: Randomized to 24 weeks of oral relugolix 40 mg once daily co-administered with 1.0 mg estradiol and 0.5 mg norethindrone acetate in the parent study;
 
Parent Study Group B: Randomized to 12 weeks of oral relugolix 40 mg once daily followed by 12 weeks of oral relugolix 40 mg once daily co-administered with 1.0 mg estradiol and 0.5 mg norethindrone acetate in the parent study;
 
Parent Study Group C: Randomized to placebo in the parent study.
 
 
The parent study Baseline will be used as the reference point for this extension study for all change from baseline-related endpoints. The pain scores during the Baseline Pain Assessment Period of the parent study will establish the patient's baseline for both the parent study and the extension study.
 
Primary Efficacy Endpoints
 
 
Proportion of women who respond or maintain response at Week 52/Early Termination, based on their dysmenorrhea NRS scores;
 
Proportion of women who respond or maintain response at Week 52/Early Termination, based on their NMPP NRS scores.
 

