**Efficacy**

Efficacy data will be summarized by the original randomized treatment group assigned in the parent study (ie, Parent Study Groups A, B, and C) for the mITT Population. The analyses methods for efficacy endpoints are similar to those used for the parent studies, unless otherwise specified in the statistical analysis plan (SAP).

The point estimate and 2-sided 95% confidence interval (CI) for the primary efficacy endpoints (proportion of responders based on dysmenorrhea NRS scores and use of rescue analgesic medications, proportion of responders based on NMPP scores and use of rescue analgesic medications) will be calculated.

The methods for analyzing the additional efficacy endpoints are described in the SAP.

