## 3. STUDY OBJECTIVES AND ENDPOINTS

Descriptive assessments of long-term efficacy and safety will be made between the parent study Baseline and the end of the extension study (Week 52) for the following parent study treatment groups:

- Parent Study Group A: Randomized to 24 weeks of oral relugolix 40 mg once daily co-administered with 1.0 mg estradiol and 0.5 mg norethindrone acetate in the parent study;
- Parent Study Group B: Randomized to 12 weeks of oral relugolix 40 mg once daily followed by 12 weeks of oral relugolix 40 mg once daily co-administered with 1.0 mg estradiol and 0.5 mg norethindrone acetate in the parent study;
- Parent Study Group C: Randomized to placebo in the parent study.

The parent study Baseline will be used as the reference point for this extension study for all change from baseline-related endpoints. The pain scores during the Baseline Pain Assessment Period of the parent study will establish the patient's baseline for both the parent study and the extension study.

In women with endometriosis-associated pain, the study objectives and corresponding endpoints are as follows:

Objectives	Endpoints
------------	-----------

Objectives	Endpoints
Primary Efficacy	

 
• To evaluate long-term efficacy of relugolix 40 mg once daily co-administered with low-dose estradiol and norethindrone acetate for up to 52 weeks, among patients who previously completed a 24-week treatment period in one of the parent studies (MVT-601-3101 or MVT-601-3102), on endometriosis-associated pain.
 
	
 
• Proportion of women who respond or maintain response at Week 52/Early Termination, based on their dysmenorrhea Numerical Rating Scale (NRS) scores;
 
• Proportion of women who respond or maintain response at Week 52/Early Termination, based on their NMPP NRS scores.
 

Secondary Efficacy	

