### **9.3. Sample Size Justification**

Because this is an extension study, the sample size will be determined by the number of patients who have completed a parent study and who are eligible and willing to participate in the extension study. It is estimated that approximately 800 patients (67% of the total of 1200 patients who will be randomized into the parent studies) will participate in this study.

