### **9.4. Efficacy Analyses**

Unless otherwise specified, efficacy analyses will be conducted using the mITT Population.

Efficacy endpoints will be summarized by the original treatment groups assigned in the parent study.

The point estimates and 2-sided 95% confidence intervals (CI) for the primary efficacy endpoints (proportion of responders based on dysmenorrhea NRS scores and use of rescue analgesic medications, proportion of responders based on NMPP scores and use of rescue analgesic medications) will be calculated.

A responder at a given time point and for a specific type of pain (dysmenorrhea or NMPP) is defined as a patient who had a reduction in that type of pain from Baseline greater than or equal to a pre-determined threshold and who did not have an increase in the use of rescue analgesic medications for endometriosis-associated pain compared with the use at Baseline. Patients who had a pain reduction less than the pre-determined threshold or who had an increase in the use of analgesics for endometriosis-associated pain will be considered non-responders. The pain reduction thresholds will be determined for NMPP and dysmenorrhea separately (see the SAP for details) for the parent studies and these same thresholds will be applied to this study.

Baseline values are calculated using the Baseline pain assessment period, which is defined as the period from the date of the first dose of placebo in the parent study Run-In Period through the day prior to the first dose of randomized study drug. Patients' average NRS pain scores and use

of rescue analgesic medications for endometriosis-associated pain (dysmenorrhea or NMPP) will be compared between a given visit-specific pain assessment period (eg, Week 28, Week 32, etc.) and the Baseline pain assessment period. The visit-specific pain assessment period is defined as the last 35 calendar days immediately prior to and including the last dose of study drug treatment received prior to the visit date.

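### The Week 52 primary responder proportions are assigned to everyone randomized and dosed in the parent studies, although the objective concerns 24-week completers and about a third of that planned denominator would never enter the extension

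*Protocol*

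**What the plan says.** Section 9.2 (Amendment 1) names mITT as the basis for the efficacy analyses. The population is there "defined as all patients who were randomized in a parent study (MVT-601-3101 or MVT-601-3102) and who have received any amount of randomized study drug". Entry into the extension is not a condition. Section 9.4 makes this the default: "Unless otherwise specified, efficacy analyses will be conducted using the mITT Population". The synopsis, under Efficacy, says the same, with results summarized by original treatment group ("ie, Parent Study Groups A, B, and C) for the mITT Population").

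The two primary endpoints are "Proportion of women who respond or maintain response at Week 52/Early Termination, based on their dysmenorrhea NRS scores" and "Proportion of women who respond or maintain response at Week 52/Early Termination, based on their NMPP NRS scores". No separate population is given for either.

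The primary objective in the synopsis is long-term efficacy up to Week 52, to be evaluated "among patients who previously completed a 24-week treatment period in one of the parent studies (MVT-601-3101 or MVT-601-3102), on endometriosis-associated pain". The synopsis study design also fixes who is in the extension: "The administration of the first dose of study drug for MVT-601-3103 will define enrollment into this study". Section 9.3 gives the expected number: "approximately 800 patients (67% of the total of 1200 patients who will be randomized into the parent studies) will participate in this study".

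For the bone mineral density threshold test, the synopsis does restrict the analysis, to Group A women who also enrolled in the extension. Section 9.5 repeats the test without restating that condition. Section 9.4 leaves derivations and missing-data handling to the SAP.

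**The concern.** The stated population and the stated question do not match. The mITT denominator holds two kinds of women whom the extension never observes: those who left a parent study before Week 24, who fall outside the wording of the objective, and those who completed 24 weeks but took no extension drug, for whom there is no treatment up to Week 52 to evaluate. The protocol does not say how the non-entrants divide between the two.

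Neither kind has a Week 52 or Early Termination visit under this protocol. The 35-day pain window in Section 9.4 is tied to a visit date, so it has nothing to attach to. The primary result is a single proportion with a 95% confidence interval for each parent group and no formal comparison, so its meaning rests largely on who is in the denominator. If a third of that denominator has no extension data, a reader cannot tell whether the figure describes durability of response, retention into the extension, or parent-study status.

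**Working it through.** **Inputs from the protocol.** 1200 women randomized in the parent studies and about 800 expected in the extension (Section 9.3); mITT requires parent randomization and at least some randomized drug (Section 9.2); enrolment means the first extension dose (synopsis).

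**Inputs assumed, because the protocol gives none.** Share randomized but never dosed, f = 0-5%; response among entrants, p = 60-80%; response credited to non-entrants, q = 0 to p.

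**1. The protocol's own figure.** 800/1200 = 66.7%, which rounds to the stated 67%.

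**2. Non-entrants in the planned denominator.** 1200 − 800 = 400, and 400/1200 = 33.3%. The 1200 counts randomized women, whereas mITT also requires dosing. With N = 1200(1 − f), the share is (N − 800)/N:

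| Never dosed (assumed) | N | Non-entrants | Share |
|---|---|---|---|
| 0% | 1200 | 400 | 33.3% |
| 1% | 1188 | 388 | 32.7% |
| 2% | 1176 | 376 | 32.0% |
| 5% | 1140 | 340 | 29.8% |

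**3. Effect on the proportion, by scoring rule.** If all are kept in the denominator, the mITT proportion is (800p + 400q)/1200:

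| p (entrants) | q = 0 | q = 30% | q = 50% | q = p |
|---|---|---|---|---|
| 60% | 40.0% | 50.0% | 56.7% | 60% |
| 70% | 46.7% | 56.7% | 63.3% | 70% |
| 80% | 53.3% | 63.3% | 70.0% | 80% |

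- *Non-entrants as non-responders (q = 0):* the proportion falls by 20.0, 23.3 and 26.7 points. The result then partly measures parent-study dropout and non-enrolment.
- *Parent status carried forward (q > 0):* the table shows falls of 3.3 to 16.7 points for q = 30-50%. By the formula there is no change if q = p and a rise if q exceeds p. Results from Week 24 or earlier are reported as Week 52; within Group C these are placebo-only results.
- *Non-entrants excluded as unobserved:* the proportion is p on about 800 women, but this is not the mITT analysis that Section 9.2 states.

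**4. Precision.** Assume three equal groups: 400 randomized and 800/3 ≈ 267 entrants per group. The 95% half-width is 1.96 × √(p(1 − p)/n). At p = 75% with n = 267 it is 5.2 points. Keeping all 400, with q between 0 and 60%, gives mixed proportions of (2/3)(75%) + (1/3)q = 50% to 70%, and half-widths of 4.9 to 4.5 points. The difference is about 0.3 to 0.7 points.

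**The case against.** The strongest reply has four parts.

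**The text may be superseded.** Sections 9.2 to 9.4 are quoted from Amendment 1. Amendments 2, 3 and 3.1 are listed; the next version is only partly shown and its Section 9 is absent. Its visible synopsis still states the Week 52 objective among 24-week completers and adds Week 104, but whether the population changed cannot be known. This stands, and it limits confidence.

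**The SAP may settle it.** Section 9.4 opens with a qualifier that allows another population, and scoring is left to the SAP. This stands for the size and direction of the effect. It does not remove the mismatch: Section 9.2 fixes the efficacy population itself, its deference to the SAP concerns analysis methods, and no exception for the primary endpoints appears in the document.

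**A parent-based population has a purpose.** Section 9 presents measures over both studies by parent group, and restricting to entrants conditions on completing treatment and passing re-entry criteria. This supports keeping mITT for displays over the whole 52 weeks. It does not justify non-entrants in the denominator of a Week 52 proportion about 24-week completers.

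**Stronger readings go too far.** A reader might infer that a third of the Week 52 result comes from women never on extension drug. The document shows only a third of the planned denominator, because exclusion as unobserved remains possible. A reader might also infer that placebo outcomes contaminate a 52-week relugolix estimate. Results are given by parent group, so Group C never enters Groups A or B, and Group C could have at most 28 weeks of relugolix by Week 52. Nor is the interval seriously too narrow: the gap in the scenarios above is under one point. Finally, counting women who stop during the extension by their Early Termination status follows from the endpoint's label, not from the population definition, and is a separate question.

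**Conclusion.** The point holds as a mismatch between a stated rule and its own question: as written in Amendment 1, the population for the primary Week 52 proportions is wider than the objective, by about 400 of 1200 planned women (33%, or about 30% if as many as 5% were never dosed). The consequence is conditional. With non-entrants as non-responders, the loss is 20-27 points at an assumed 60-80% response among entrants; under other rules it may be smaller, nil or in the opposite direction. A bias in favour of the treatment is not shown.

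The 1200 and 800 are planning figures, and the response rates and equal allocation are assumptions. Confidence is moderate because neither the SAP nor Section 9 of the later amendments is shown.

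**What to change.** First check Section 9 of the later amendments. If the definition is unchanged:

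- In Sections 9.2 and 9.4 and the synopsis, define an Extension Population: women randomized in a parent study who took at least one dose of MVT-601-3103 study drug.
- Use it, by parent group, for the two primary endpoints and the other Week 52 efficacy endpoints. This matches the restriction that the synopsis already places on the bone mineral density threshold test.
- Keep the parent-based mITT population as supportive, for the displays from parent Baseline to Week 52.

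The cost is wording in three places and a second set of supportive tables. The denominator is smaller, so intervals are slightly wider, and the estimate is conditional on entering the extension, which the report should say.

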### **9.3. Sample Size Justification**

Because this is an extension study, the sample size will be determined by the number of patients who have completed a parent study and who are eligible and willing to participate in the extension study. It is estimated that approximately 800 patients (67% of the total of 1200 patients who will be randomized into the parent studies) will participate in this study.

### **9.4. Efficacy Analyses**

Unless otherwise specified, efficacy analyses will be conducted using the mITT Population.

Efficacy endpoints will be summarized by the original treatment groups assigned in the parent study.

The point estimates and 2-sided 95% confidence intervals (CI) for the primary efficacy endpoints (proportion of responders based on dysmenorrhea NRS scores and use of rescue analgesic medications, proportion of responders based on NMPP scores and use of rescue analgesic medications) will be calculated.

A responder at a given time point and for a specific type of pain (dysmenorrhea or NMPP) is defined as a patient who had a reduction in that type of pain from Baseline greater than or equal to a pre-determined threshold and who did not have an increase in the use of rescue analgesic medications for endometriosis-associated pain compared with the use at Baseline. Patients who had a pain reduction less than the pre-determined threshold or who had an increase in the use of analgesics for endometriosis-associated pain will be considered non-responders. The pain reduction thresholds will be determined for NMPP and dysmenorrhea separately (see the SAP for details) for the parent studies and these same thresholds will be applied to this study.

Baseline values are calculated using the Baseline pain assessment period, which is defined as the period from the date of the first dose of placebo in the parent study Run-In Period through the day prior to the first dose of randomized study drug. Patients' average NRS pain scores and use

of rescue analgesic medications for endometriosis-associated pain (dysmenorrhea or NMPP) will be compared between a given visit-specific pain assessment period (eg, Week 28, Week 32, etc.) and the Baseline pain assessment period. The visit-specific pain assessment period is defined as the last 35 calendar days immediately prior to and including the last dose of study drug treatment received prior to the visit date.

For any pain assessment period (Baseline or visit-specific), the average NRS scores will be calculated for dysmenorrhea and NMPP separately. An average NRS score for dysmenorrhea is calculated as the average NRS score over the days with menses during a given pain assessment period. An average NRS score for NMPP is calculated as the average NRS score over the days without menses during a given pain assessment period. The analgesic use for a given pain assessment period is summarized by total dose count defined as the average daily dose count taken during the given pain assessment period multiplied by 35. Additional details on calculating dose counts and on the precise definition of an increase in analgesic use will be provided in the SAP.

Descriptive statistics will be provided for efficacy endpoints (listed below) similar to those used for the parent studies.

- Change from the parent study Baseline to Week 52 in the EHP-30 Pain Domain scores;
- Change from the parent study Baseline to Week 52/EOT in the mean dysmenorrhea NRS score;
- Proportion of patients who are better or much better on the PGIC for dysmenorrhea at Week 52/EOT;
- Change from the parent study Baseline to Week 52/EOT in the mean NMPP NRS score;
- Proportion of patients who are better or much better on the PGIC for NMPP at Week 52/EOT;
- Change from the parent study Baseline to Week 52/EOT in the mean dyspareunia NRS scores;
- Proportion of patients who are better or much better on the PGIC for dyspareunia at Week 52/EOT;
- Change from the parent study Baseline to Week 52/EOT in the mean dyspareunia functional impairment on the sB&B scale;
- Change from the parent study Baseline to Week 52/EOT in severity scores on the PGA for pain;
- Proportion of responders at Week 52/EOT based on EHP-30 Pain Domain scores;
- Change from the parent study Baseline to Week 52/EOT in function impairment on the PGA for function;
- Change from the parent study Baseline to Week 52/EOT in each of the non-pain EHP-30 domains (Control and Powerlessness, Social Support, Emotional Well-Being, and Self-Image);
- Change from the parent study Baseline pain assessment period to Week 52/EOT in dysmenorrhea-related functional effects (sB&B);
- Change from the parent study Baseline pain assessment period to Week 52/EOT in NMPP-related functional effects (sB&B).

For binary endpoints, the point estimate and 2-sided 95% CI for the proportion will be provided by parent study treatment group.

For endpoint of proportion of responders at Week 52/EOT based on EHP-30 Pain Domain scores, a responder is defined using the same within-patient score change threshold determined from the parent studies.

Details on the endpoint analyses including derivations, handling of missing data, and statistical methods will be provided in the SAP.

